9.3 VARIABLES

9.3.1 Exposures

Exposure of this study is defined as new initiation of Tio/Olo during the study period between 1st January 2014 and 31st December 2019. The duration of exposure is defined as the period between the index date and the end of follow-up which is described in section 9.7.1.

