9.5 STUDY SIZE

There will be around 4,000 patients using Tio+Olo in the Taiwan NHIRD that can be enrolled in this study.

Assuming that observed incidence rates of each AE from Ferguson paper could be replicated, and 4000 patients were enrolled in the study in a uniform distribution from 0 to 6 years. The estimation and 95% CI for incidence rate of each AE among new users of Spiolto® Respimat® for the study duration of 6 years were calculated based on Poisson distribution and provided as the following table.

Table 1 Incidence rate of AEs

Adverse events	Incidence	N	95% CI	
	rate per		Lower	Upper
	100			
	patient			
	years			
Pneumonia	4.69	4000	4.308	5.083
COPD	55.42	4000	54.092	56.758
exacerbation				
Arrhythmia	1.82	4000	1.583	2.067
Supraventricul	1.16	4000	0.975	1.358
ar tachycardia				

001-MCS-90-118_RD-23 (2.0) / Saved on: 03 Jul 2020

NIS Protocol Page 25 of 43 BI Study Number: 1237-0109 c38644780-01

Proprietary confidential information © 2022 Boehringer Ingelheim International GmbH or one or more of its affiliated companies

Incidence rate of AEs from Ref: G.T. Ferguson, et al., Respiratory Medicine 143 (2018) 67–73.

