9.7.1 Main analysis

All variables, including patient characteristics, baseline measures, and outcomes, will be analysed descriptively.

- For all analyses, variables will be reported as follows: Continuous variables (e.g., age) will be presented as means (with standard deviation, SD) and/or medians (with interquartile range, IQR), minimum, maximum.
- Categorical variables (e.g., sex) will be presented as absolute and relative frequencies.

We will first describe formation of the study cohort. Patient characteristics at baseline will be described using standard descriptive statistics. Absolute standardized differences (ASDs) will be used to compare the characteristics between the two groups, in which a >0.1 ASD indicates a meaningful difference.

As an objective of the study was to compare the clinical attributes of patients in each study group. The standardized difference will be used as a parameter to quantify the between-group differences for each clinical attribute. This is metric is commonly used in studies utilizing secondary health data, in which a standardized difference of larger than 0.1 indicates a meaningful difference with respect to the clinical attribute between the two study groups.

For the analysis of primary outcome, the incidence rates of AEs during entire followup period will be calculated based on the following formula:

NIS Protocol Page 26 of 43 BI Study Number: 1237-0109 c38644780-01

Proprietary confidential information © 2022 Boehringer Ingelheim International GmbH or one or more of its affiliated companies

(Total number of patients in the Tio+Olo cohort experiencing an event of interest for the first time during the given time period) / (Total person-time at risk from current use of Tio+Olo during the given period)

For the analysis of the primary outcome, individuals will be followed up from the index date until the earliest of the date of the follows, whichever occurs first 1) disenrollment; 2) the end of the study period; 3) death; 4) discontinuation of the index drug; 5) adding ICS mono on top of Tio/Olo.

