9.1.1 Exposure? (e.g. pharmacy dispensing, general practice prescribing, claims data, self-report, face-to- face interview)				9.4
9.1.2 Outcomes? (e.g. clinical records, laboratory markers or values, claims data, self-report, patient interview including scales and questionnaires, vital statistics)				9.4
9.1.3 Covariates and other characteristics?				9.4
9.2 Does the protocol describe the information available from the data source(s) on:				
9.2.1 Exposure? (e.g. date of dispensing, drug quantity, dose, number of days of supply prescription, daily dosage, prescriber)				9.3.1
9.2.2 Outcomes? (e.g. date of occurrence, multiple event, severity measures related to event)	\boxtimes			9.3.2
9.2.3 Covariates and other characteristics? (e.g. age, sex, clinical and drug use history, comorbidity, co-medications, lifestyle)				9.3.3
9.3 Is a coding system described for:				
9.3.1 Exposure? (e.g. WHO Drug Dictionary, Anatomical Therapeutic Chemical (ATC) Classification System)		\boxtimes		
9.3.2 Outcomes? (e.g. International Classification of Diseases (ICD), Medical Dictionary for Regulatory Activities (MedDRA))		\boxtimes		
9.3.3 Covariates and other characteristics?		\boxtimes		
9.4 Is a linkage method between data sources described? (e.g. based on a unique identifier or other)	\boxtimes			9.4
Comments:				
9.3 Details will be described in SEAP.				

NIS Protocol BI Study Number: 1237-0109 Page 38 of 43 c38644780-01

Section 10: A	nalysis plan	Yes	No	N/A	Section
					Number
	tatistical methods and the r their choice described?				9.7
10.2 Is study s estimated	size and/or statistical precision d?				9.5
10.3 Are descr	iptive analyses included?	\square			9.7.1
10.4 Are strati	fied analyses included?	\square			9.7.2
	plan describe methods for ontrol of confounding?				
	plan describe methods for control of outcome cication?				
	plan describe methods for missing data?				
10.8 Are relevated described	ant sensitivity analyses ?				9.7.2
Comments:					
			1		
Section 11: Do	ata management and quality	_ Yes	No	N/A	Section Number
data stora	protocol provide information on age? (e.g. software and IT t, database maintenance and anti-fraudarchiving)				
11.2 Are methodescribed	ods of quality assurance ?				9.8
	system in place for ent review of study results?			\boxtimes	

Comments:

NIS Protocol Page 39 of 43 BI Study Number: 1237-0109 c38644780-01

11.1 Details will be described in DMRP.				
Section 12: Limitations	Yes	No	N/A	Section Number

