6.3 STUDY POPULATION

For incident Tio/Olo combined inhaler cohort

• Inclusion criteria:

- 1. At least one prescription for Tio+Olo (fixed dose combination (FDC) or free combination) as a new initiation between 1st January 2014 and 31st December 2019 (the free combination will be defined as the prescriptions of the two compounds on the same day);
- 2. Aged ≥ 40 years on the index date (The first dispensing of Tio+Olo combined inhaler will be defined as the index date);
- 3. At least one diagnosis of COPD (ICD9: 491.x, 492.x, 496; ICD10: J41.x, J42, J43.x, J44.x) at any time prior to or on the index date;
- 4. At least one year of continuous medical and health insurance plan prior to the index date will be required to allow for a look-back period for the covariates and identification of new use of the study drugs;
- 5. At least one record in the health insurance system database.

• Exclusion criteria:

- 1. Any use of Tio+Olo in free or fixed form within one year prior to the index date. (the free combination will be defined as the prescriptions of the two compounds within 30 days);
- 2. Individuals with asthma, allergic rhinitis, lung cancer, interstitial lung disease, or lung transplant identified at any time prior to the index date.

Relevant ICD codes and procedure code are provided in the Annex.

Statistical and Epidemiological Analysis Plan (SEAP) for Non-Interventional Studies (NIS) Template c40431892-01 Page 7 of 38

Proprietary confidential information © 2022 Boehringer Ingelheim International GmbH or one or more of its affiliated companies

For other incident LAMA/LABAs combined inhaler cohort

Inclusion criteria:

- 1. At least one prescription for LAMA+LABA FDC (Vilanterol/Umeclidinium; Indacaterol /Glycopyrronium) or free combination (LABA: Salmeterol; Formoterol; Procaterol; Indacaterol; Olodaterol, LAMA: Tiotropium bromide; Glycopyrrolate; Umeclidinium) other than Tio/Olo as a new initiation between 1st January 2014 and 31st December 2019 (the free combination will be defined as the prescriptions of the two compounds on the same day);
- 2. Aged ≥ 40 years on the index date (The first dispensing of LAMA+LABA combined inhaler will be defined as the index date);
- 3. At least one diagnosis of COPD at any time prior to or on the index date;

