10. DATA ANALYSIS

10.1 MAIN ANALYSIS

All variables, including patient characteristics, baseline measures, and outcomes, will be analyzed descriptively.

- For all analyses, variables will be reported as follows: Continuous variables (e.g., age) will be presented as means (with standard deviation, SD) and/or medians (with interquartile range, IQR), minimum, maximum.
- Categorical variables (e.g., sex) will be presented as absolute and relative frequencies.

We will first describe formation of the study cohort. Patient characteristics at baseline will be described using standard descriptive statistics. Absolute standardized differences (ASDs) will be used to compare the characteristics between the two groups, in which a >0.1 ASD indicates a meaningful difference.

As an objective of the study was to compare the clinical attributes of patients in each study group. The standardized difference will be used as a parameter to quantify the between-group differences for each clinical attribute. This is metric is commonly used in studies utilizing

Statistical and Epidemiological Analysis Plan (SEAP) for Non-Interventional Studies (NIS) Template

c40431892-01 Page 15 of 38

Proprietary confidential information © 2022 Boehringer Ingelheim International GmbH or one or more of its affiliated companies

secondary health data, in which a standardized difference of larger than 0.1 indicates a meaningful difference with respect to the clinical attribute between the two study groups.

For the analysis of primary outcome, the incidence rates of AEs during entire follow-up period will be calculated based on the following formula:

(Total number of patients in the Tio+Olo cohort experiencing an event of interest for the first time during the given time period) / (Total person-time at risk from current use of Tio+Olo during the given period)

[figure not shown]
Number of at-risk patients will be defined for specific adverse outcome of interest, taking into account whether it is a chronic condition for which patients with a prevalent condition are not considered at risk.

For the analysis of the primary outcome, individuals will be followed up from the index date until the earliest of the following

- 1) Outcome of interest
- 2) disenrollment;
- 3) the end of the study period;
- 4) death;
- 5) discontinuation of the index drug use as a lapse of 45 days without subsequent prescription;
- 6) adding ICS mono on top of Tio/Olo.

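### Follow-up does not end at a switch, and the 45-day lapse rule is incomplete, so the Tio/Olo rates can include time and events on another LAMA/LABA or off drug

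*SAP*

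**What the plan says.** The denominator in SAP 10.1 is "Total person-time at risk from current use of Tio+Olo during the given period". Protocol 9.3.1 makes exposure and follow-up the same interval: "The duration of exposure is defined as the period between the index date and the end of follow-up". Whatever ends follow-up therefore decides what counts as current use.

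SAP 7.2.1 and 10.1 give the same six end points. The two that concern treatment are "discontinuation of the index drug use as a lapse of 45 days without subsequent prescription" and "adding ICS mono on top of Tio/Olo". Protocol 9.7.1 is shorter still: "4) discontinuation of the index drug; 5) adding ICS mono on top of Tio/Olo". Starting another LAMA/LABA is on neither list, although SAP 6.3 names those products for the comparison cohort.

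Entry is dated by dispensing (SAP 6.3: "The first dispensing of Tio+Olo combined inhaler will be defined as the index date"), while the lapse is worded in terms of prescriptions. No readable text gives a supply length, the day on which the 45 days begin, or whether follow-up is cut at the start or the end of the lapse.

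**The concern.** The formula promises an on-treatment rate, but the rule that limits person-time is not tied to treatment held by the patient. A patient who moves from Tio/Olo to another LAMA/LABA stays in the Tio/Olo cohort until the lapse completes. Any pneumonia, arrhythmia or death in that window is then booked to Tio/Olo. A patient who simply stops is handled in the same way.

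Almost every line of SAP Table 2 rests on this person-time, so the issue reaches the whole primary result. Reproducibility suffers too. SAP 11 has a second analyst review or repeat the analytic approach, yet two programmers could follow SAP 10.1 faithfully and give the same single-fill patient 45 or 75 days, assuming a 30-day supply.

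**Working it through.** **Inputs.** Lapse of 45 days (SAP 7.2.1 and 10.1). Supply length *s* and refill pattern: not in the documents, so *s* = 14, 28, 30, 60 and 90 days are assumed. Study-size inputs (Protocol 9.5): "4000 patients were enrolled in the study in a uniform distribution from 0 to 6 years", with Poisson limits.

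**Step 1: the plan's own person-time figure.** Mean follow-up is 3 years, so 4,000 × 3 = 12,000 person-years. Expected events = rate × 12,000/100. The limits are the 2.5% and 97.5% quantiles of that Poisson distribution, divided by 120 to give rates per 100 patient-years.

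- Pneumonia: mean 4.69 × 120 = 562.8; 517/120 = 4.308 and 610/120 = 5.083.
- COPD exacerbation: 6,491/120 = 54.092 and 6,811/120 = 56.758.
- Arrhythmia: 190/120 = 1.583 and 248/120 = 2.067.
- Supraventricular tachycardia: 117/120 = 0.975 and 163/120 = 1.358.

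All eight limits match, so no printed figure is wrong. The table applies no discontinuation rule and cannot settle how the lapse is meant.

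**Step 2: two readings that count the lapse days.**

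- Reading A: the 45 days run from the last prescription date and follow-up ends on day 45. Off-drug days counted = 45 − *s* if *s* < 45; on-drug days lost = *s* − 45 if *s* > 45.
- Reading B: the 45 days run from the end of supply and follow-up ends on day 45 of the gap. Off-drug days counted = 45 for every *s*; no on-drug days are lost.

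For one fill:

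| Assumed *s* | A: counted | A: off drug | A: on-drug lost | B: counted | B: off drug |
|---|---|---|---|---|---|
| 14 | 45 | 31 | 0 | 59 | 45 |
| 28 | 45 | 17 | 0 | 73 | 45 |
| 30 | 45 | 15 | 0 | 75 | 45 |
| 60 | 45 | 0 | 15 | 105 | 45 |
| 90 | 45 | 0 | 45 | 135 | 45 |

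**Step 3: share of counted time, *s* = 30.**

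- One fill: A, 15/45 = 33%; B, 45/75 = 60%.
- Twelve fills, each refilled on the day of run-out: A, 11 × 30 + 45 = 375 days, 15/375 = 4%; B, 12 × 30 + 45 = 405 days, 45/405 = 11%.

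The single-fill shares are extremes. The overall figure depends on the mix of short and long users, which is unknown.

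**Step 4: a switch.** If another LAMA/LABA starts on day *d* after the last Tio/Olo fill, the days on the other product counted as Tio/Olo are 45 − *d* under A and (*s* + 45) − *d* under B. With *s* = 30 and *d* = 30 this is 15 and 45 days. The end-of-follow-up lists do not stop this under either reading.

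**Step 5: cutting at the start of the lapse.** If follow-up is backdated to a lapse that starts at the end of supply, no off-drug grace days are counted. If it is backdated to a lapse that starts at the last prescription, the whole of the last supply is dropped, whatever its length. The censoring date therefore matters as much as the start of the 45 days.

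**Step 6: direction.** The computed rate is (E_on + E_off)/(T_on + T_off), where E is events and T is person-time. It exceeds the on-drug rate only if E_off/T_off > E_on/T_on. Nothing in the documents fixes that ordering, and it may differ by event.

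**The case against.** A reader might infer that the rule biases the denominator in both directions as a matter of fact: off-drug time added for short supplies, on-drug time lost for long ones. The documents do not support that. They are silent on the start of the lapse, and silence is not a definition. Where lapse days are counted, on-drug time is lost only if the 45 days run from the prescription date and supplies exceed 45 days. No supply length is stated.

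Other points on the plan's side:

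- A switch is not ignored altogether. Tio/Olo prescriptions stop, so the lapse eventually ends follow-up. This stands, and it limits the misattributed time without removing it.
- Counting some grace days is a legitimate analyst's choice, and the rates are descriptive, with no adverse-event comparison between drugs. This also stands. The choice still has to be stated.
- The mix of dispensing and prescription may be loose wording, since SAP 6.3 uses both for the same entry. One cannot conclude that two date systems are intended.
- The checklist entry in Protocol Annex 2 that mentions quantity and days of supply lists examples only, so nothing here rests on it.
- SAP 10.2 and Protocol 9.7.2 cannot be read, and figures beside the follow-up rules are not shown. A sensitivity analysis or follow-up diagram may be there. That is not counted against the plan, but the readable main rule still needs completing.

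**Conclusion.** The point holds as a defect of definition with a conditional numerical effect. If lapse days are counted, the Tio/Olo rates include off-drug days and, after a switch, days and events on another LAMA/LABA. That does not match a denominator described as current use. With an assumed 30-day supply, the off-drug excess after the last fill is 15 days if the lapse runs from the prescription date (33% of counted time for one fill, about 4% for 12 consecutive fills). It is up to 45 days if the lapse runs from the end of supply. These figures rest on assumed supply lengths and, for repeat fills, on refills without gaps. No direction of bias can be claimed, and no figure printed in the plan is wrong. The change should be made before the rates are computed.

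**What to change.** In SAP 7.2.1 and 10.1, as an analysis definition only, with no implication for how patients are treated:

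(a) Add the first dispensing of another LAMA/LABA in place of Tio/Olo as an end-of-follow-up event.

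(b) Build exposure from dispensing date plus days supplied. Use the 45-day gap only to identify discontinuation, and count it from the end of supply. Use dispensing as the term throughout.

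(c) Fix one censoring date in advance. Report the rates with person-time and events cut at the end of supply alongside those with grace days included, unless the unreadable SAP section already does so. This step is needed because (b) alone, with grace days counted, would leave 45 off-drug days after the last fill at every supply length.

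Cost: SAP wording, some programming and one extra table, provided the days-supplied field is in the extract. Expect somewhat fewer person-years and events, and slightly wider confidence intervals.

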10.3 SAFETY ANALYSIS

Not applicable.

11. QUALITY CONTROL

The study will strictly follow relevant BI SOPs. In addition, this study will follow key elements of the Guideline for Good Pharmacoepidemiology Practices (GPP) and the Guideline for Good Pharmacovigilance Practices (GVP).

The statistical analytic approach will be reviewed/repeated by a second analyst to ensure quality control. The study report will be reviewed, approved and archived per BI SOP.

ANNEX 1. ADDITIONAL INFORMATION

Table 1. Demographic and cohort entry of the Tio/Olo cohort and LAMA/LABA cohort

	Tio/Olo cohort N=xxxx		LAMA/LABA coho N=xxxx	
	N	%	N	%
Gender				
Male				
Female				
Age				
Mean, SD				
40~59				
60~79				
80+				
Calendar year of cohort entry				
2014				
2015				
2016				
2017				
2018				
2019				
Season of cohort entry date				
Spring (Mar-May)				
Summer (Jun-Aug)				
Fall (Sep-Nov)				
Winter (Dec-Feb)				

Statistical and Epidemiological Analysis Plan (SEAP) for Non-Interventional Studies (NIS) Template

c40431892-01 Page 20 of 38

Table 2. Incidence rate of adverse events in patients with COPD treated with Tio+Olo

Adverse event	No. of events	Person-Years	Incidence rate (per 100 000 person year)	95% CI
Potentially recurrent events				
Nasopharyngitis				
Pneumonia				
Moderate COPD exacerbation				
Severe COPD exacerbation				
Constipation				
Diarrhoea				
Urinary retention				
Urinary tract infection				
Urticaria				
Rash				
Incident events (no occurrence o	f corresponding	g codes during t	the 1-year baselin	ie period)
Arrhythmia				
Myocardial ischemia				
Supraventricular tachycardia				
Glaucoma				
Nonfatal myocardial infarction				
Nonfatal hemorrhagic stroke				
Nonfatal ischemic stroke				
Nonfatal Acute, but ill-				
defined, cerebrovascular				
disease				
Death				

Statistical and Epidemiological Analysis Plan (SEAP) for Non-Interventional Studies (NIS) Template

c40431892-01 Page 21 of 38

Table 3. Secondary outcome (baseline comparison between two study groups)

- ,		1			J & 1)
	Tio/Ol/	o cohort	LAM	A/LABA	
		XXXX	со	hort	Standardized
			N=	XXXX	difference
	N	%	N	%	
COPD treatments in 1 year prior to inde	ex date				
LAMA					
LABA					
ICS					
ICS+LABA free combination					
ICS+LAMA free combination					
LAMA+LABA free combination					
ICS+LAMA+LABA free combination					
ICS/LABA FDC					
LAMA/LABA FDC					
ICS/LAMA/LABA FDC					
Use of other respiratory drugs in 1 year	prior to	index			
date					
Mucolytics					
Theophylline					
Short-acting beta-agonists (SABA)					
Short-acting muscarinic antagonists					
(SAMA)					
Acute COPD exacerbation in 1 year prior	or to inde	x date			
Moderate exacerbation					
0					
1					
>=2					
Severe exacerbation					
0					
1					
>=2					
All exacerbations (Moderate +					
Severe)					
0					
1 >=2					
	c prior to	indov			
Acute COPD exacerbation in the 30 day date	s prior to	inuex			
Moderate exacerbation					
0 1					
>=2					
Severe exacerbation					
Severe exacerbation					

Statistical and Epidemiological Analysis Plan (SEAP) for Non-Interventional Studies (NIS) Template

c40431892-01 Page 22 of 38

	Tio/Olo cohort N=xxxx		LAM	A/LABA	
				hort	Standardized
	N=X	(XXX	N=	XXXX	difference
	N	%	N	%	_
0					
1					
>=2					
All exacerbations (Moderate +					
Severe)					
0					
1					
>=2					
Hospitalizations caused by exacerbation	of COPE	in 1 year p	rior to i	ndex date	
0					
1					
>=2					
All-cause hospitalizations in 1 year prior	r to index	date			
0					
1					
>=2					
Comorbidities:					
Cardiovascular disease					
Cerebrovascular disease					
Diabetes					
Chronic kidney disease					
Pneumonia					
Cancer					
Cirrhosis					
Charlson Comorbidity Index (CCI)					
(mean, SD)					
History of medications dispensed in 1 ye	ear prior	to index			
date					
Cardiovascular drugs:					
Antihypertensives					
Antiarrhythmics					
Nitrates					
Heart failure medications					
Lipid-lowering medications					
Blood glucose–lowering medications					
Anticoagulants and antiplatelet					
agents					
Antibiotics					
Antineoplastic agents					

Statistical and Epidemiological Analysis Plan (SEAP) for Non-Interventional Studies (NIS) Template

c40431892-01 Page 23 of 38

Tropricial	ry commucinia.	i iiiioiiiiatioii 🤊	9 2022 D 0CIII I	nger mgemem	international O	morr or one or m	ofe of its affiliated c	ompanies

Statistical and Epidemiological Analysis Plan (SEAP) for Non-Interventional Studies (NIS) Template

c40431892-01 Page 24 of 38

Statistical and Epidemiological Analysis Plan (SEAP) for Non-Interventional Studies (NIS) Template

c40431892-01 Page 25 of 38

Statistical and Epidemiological Analysis Plan (SEAP) for Non-Interventional Studies (NIS) Template

c40431892-01 Page 26 of 38

Statistical and Epidemiological Analysis Plan (SEAP) for Non-Interventional Studies (NIS) Template

c40431892-01 Page 27 of 38

Probrietary confidential infort	nation © 2022 Boenringer ing	emeim international Cimbri	or one or more of its affiliated	combanies

Statistical and Epidemiological Analysis Plan (SEAP) for Non-Interventional Studies (NIS) Template

c40431892-01 Page 28 of 38

Proprietary confidential information © 2022 Boehringer Ingelheim International GmbH or one or more of its affiliated companies

